11.3 Premature Study Termination	14
12. Data Analysis	14

CONFIDENTIAL

Version 1.0 Usability of the CP950 sound processor with experienced cochlear implant users.

12.1	Statistical Analysis	14
12.2	Sample Size.....	15
13.	Risk Benefit Statement	15
13.1	Benefits	15
13.2	Risks	15
14.	Good Clinical Practices Statement	15
15.	Access to Study Documents and Study Monitoring	15
16.	Quality Control and Assurance	15
17.	Institutional Review Board	16
18.	Informed Consent Process	16
19.	Confidentiality.....	16
20.	Protocol Deviations and Amendments.....	16
21.	Data Management.....	16
22.	Record Keeping and Retention.....	17
23.	Study Report and Publication	17

CONFIDENTIAL

Version 1.0 Usability of the CP950 sound processor with experienced cochlear implant users.

1. Clinical Investigation Synopsis

Investigation title	Usability of the CP950 sound processor with experienced cochlear implant users.
Name of investigational device	CP950 Sound processor CP950 Programming Cable Adaptor Cochlear Wireless Programming Pod
Total expected duration of the clinical investigation	6 months
Enrollment period	3 months
Expected duration per subject	1 Month post CP950 Fitting
Investigational design	Single-subject usability study
Number of subjects	Up to 30 subjects
Number of investigational sites	Up to 3 sites
Inclusion criteria	
 1. At least 6 months experience with a Nucleus 24 series or later implant in at least one implanted ear 2. Subjects age 12 and older who are cognitively and developmentally able to complete all study related questionnaires as deemed by the principal investigator or delegated staff 3. At least 3 months experience with the CP810, CP920 or CP910 sound processor 4. Ability to use 2 zinc air batteries with their current MAP 5. Willingness to participate in and to comply with all requirements of the protocol for the duration of the trial
Exclusion criteria	
 1. Unrealistic expectations on the part of the subject, regarding the possible benefits, risks and limitations that are inherent to the procedure and prosthetic device 2. Additional disabilities that would prevent participation in evaluations 3. Implant types not currently supported by the

CONFIDENTIAL

Version 1.0 Usability of the CP950 sound processor with experienced cochlear implant users.

	CP950 sound processor (i.e.,N22)																		
Primary objectives	
To evaluate usability of the CP950 sound processor using the CP950 Take Home Questionnaire for existing cochlear implant users.
 
Specifically:
 
 1) Patient Reported Hearing Performance 2) Retention & Comfort 3) Ease of use 4) Use of remote controls 5) Look & feel 6) Reliability 7) Maintenance & use 																		
Additional Information	
To characterize CP950 sound processor field use data collected via Datalogging
 
To evaluate the success of wireless pairing to both the wireless programming pod and wireless accessories
																		
Investigation schedule	
  
 	Visit 1	Visit 2	
   
 Subject Enrollment & Informed Consent	X		
 
 CP950 Fitting & Programming	X	X (Datalogs)	
 
 Fit Wireless Accessories	X		
 
 CP950 Take Home Questionnaire - Subject		X	
 
 Return of the CP950 Sound Processor		X	
  
		Visit 1	Visit 2	Subject Enrollment & Informed Consent	X		CP950 Fitting & Programming	X	X (Datalogs)	Fit Wireless Accessories	X		CP950 Take Home Questionnaire - Subject		X	Return of the CP950 Sound Processor		X
	Visit 1	Visit 2																	
Subject Enrollment & Informed Consent	X																		
CP950 Fitting & Programming	X	X (Datalogs)																	
Fit Wireless Accessories	X																		
CP950 Take Home Questionnaire - Subject		X																	
Return of the CP950 Sound Processor		X																	
Primary endpoints	
Patient reported satisfaction of the CP950 sound processor as measured by the CP950 Take Home Questionnaire for existing cochlear implant users.
 
Areas of assessment:
																		

CONFIDENTIAL

Version 1.0 Usability of the CP950 sound processor with experienced cochlear implant users.

	
 1) Patient Reported Hearing Performance 2) Retention & Comfort 3) Ease of use 4) Use of remote controls 5) Look & feel 6) Reliability 7) Maintenance & use
Additional Information	
Field use data including time on air, listening environment type, and accessory use will be described.
 
The success/failure rate of wireless pairing to both the wireless programming pod and the remote microphone accessory will be quantified.

CONFIDENTIAL

Version 1.0 Usability of the CP950 sound processor with experienced cochlear implant users.

2. Abbreviations

Term	Definition
AE	Adverse Event
CRF	Case Report Form
IA	Initial Activation
IRB	Institutional Review Board
SAE	Serious Adverse Event

CONFIDENTIAL

Version 1.0 Usability of the CP950 sound processor with experienced cochlear implant users.

Page 8 of 17

CAM-CL-111_F Rev. 1

3. Introduction

Cochlear Limited's current commercial system is the Nucleus 6 (N6). This is comprised of external behind the ear (BTE) sound processors (CP910 and CP920) offering new input processing algorithms designed to improve recipients' hearing in specific situations, including background noise. The sound processors are controlled by either the remote assistant (CR230) or remote control (CR210) which avoids the user having to physically touch the sound processor. Clinicians are able to program the Nucleus 6 devices with Custom Sound 4 clinical software through either the Wireless Programming Pod or the traditional programming cable.

The CP950 Sound Processor functionality is comparable to the commercially approved Nucleus CP920 Sound Processor but in an off the ear (OTE) configuration. The processing unit, coil and magnet are integrated into one unit which is positioned directly over the magnet of the cochlear implant rather than behind the ear. The CP950 sound processor is designed to provide the same access to N6 technology including the CR210 Remote Control, the CR230 Remote Assistant as well as being compatible with the Cochlear Wireless Accessories.

Figure 1. CP950 Sound Processor

While the CP950 Sound Processor maintains the functionality of the CP920 Sound Processor, there have been a few modifications to support the OTE configuration:

- The CP950 Sound Processor only has one button while the CP920 Sound Processor has two. The ability to change volume and sensitivity for the CP950 Sound Processor will be available via either the CR230 remote assistant or CR210 remote control.
- Depending upon whether the CP950 Sound Processor is worn on the left (L) or right (R) sides of the recipients head the front and back microphones associated with wearing condition (R vs L) will need to be defined.
- As the batteries are integrated into the body of the CP950 Sound Processor they remain connected to the device when the programming cable is attached. During programming using the traditional wired Programming Pod, both the CP920 and CP950 Sound Processors are powered by the programming computer. Alternatively, due to the integrated batteries of the CP950 design, the sound processor may also be programmed via a Cochlear Wireless Programming Pod.

CONFIDENTIAL

Version 1.0 Usability of the CP950 sound processor with experienced cochlear implant users.

The primary objective of this study is to evaluate usability of the CP950 sound processor using the CP950 Take Home Questionnaire for existing cochlear implant users, specifically with regards to patient reported hearing performance, retention & comfort, ease of use, remote control use, look & feel, reliability and maintenance & use. The CP950 sound processor may provide added comfort and ease of use for recipients due to its off-the-ear configuration, smaller footprint on the head and ear, as well as its simplistic design and wireless compatibility, however; retention and patient reported hearing performance must remain acceptable.

The investigation is intended to provide the Sponsor with regional clinical experience in fitting this product on existing cochlear implant recipients prior to commercial release. The current study will evaluate the usability of the CP950 device using the CP950 Take Home Questionnaire distributed to each subject after approximately 4 weeks of take home use with the CP950 Sound Processor. Additional information such as subject datalogging and wireless pairing will also be captured. Each subject will be required to return the CP950 Sound Processor upon trial completion.

4. Study Objective

4.1 Primary Objective:

To evaluate usability of the CP950 sound processor using the CP950 Take Home Questionnaire for existing cochlear implant users. Specifically:

- 1) Patient Reported Hearing Performance
- 2) Retention & Comfort
- 3) Ease of use
- 4) Use of remote controls
- 5) Look & feel
- 6) Reliability
- 7) Maintenance & use

5. Study Design

The design is a within-subject usability study.

6. Study Length

The approximate length of the study for each subject is 1 month post CP950 sound processor fitting.

7. Device Description

The cochlear implant system that will be used in this study comprises:

- CP950 Sound processor
- CP950 Programming Cable Adaptor
- Cochlear Wireless Programming Pod.

CONFIDENTIAL

Version 1.0 Usability of the CP950 sound processor with experienced cochlear implant users.

7.1 Sound Processor Description

The CP950 Sound Processor is functionally comparable to the CP920 Sound Processor. Sharing the same ASIC chipset, the CP950 Sound Processor introduces a new form factor which integrates the processing unit, coil, coil cable and magnet into a single unit. As a result the CP950 Sound Processor will be worn in an OTE configuration positioned directly over the magnet of the cochlear implant on the recipients head rather than behind the ear.

7.2 Programming Software Description

Custom Sound version 4 will be used in this study.

8. Subject Population

8.1 Inclusion Criteria

- At least 6 months experience with a Nucleus 24 series or later implant in at least one implanted ear
- At least 3 months experience with the CP810,CP920 or CP910 sound processor
- Ability to complete study related questionnaires
- Willingness to participate in and to comply with all requirements of the protocol for the duration of the trial

8.2 Exclusion Criteria

- Unrealistic expectations on the part of the subject, regarding the possible benefits, risks and limitations that are inherent to the procedure and prosthetic device
- Additional disabilities that would prevent participation in evaluations
- Implant types not currently supported by the CP950 sound processor (i.e., N22)

8.3 Release of Medical Information

Subjects will be required to release the exchange of medical information between the Investigator(s) and the Sponsor. This requirement will be clearly identified in the Informed Consent form.

9. Investigational Procedures

9.1 Design Overview

Usability of the CP950 Sound Processor with Experienced Cochlear Implant Users will be conducted as a multi-center, prospective, single-subject usability study, evaluating the usability of the CP950 Sound Processor in existing cochlear implant recipients. A single-subject research design is appropriate since it accommodates the heterogeneity that characterizes hearing-impaired populations. Blinding procedures are not appropriate for this trial design, as it is not possible to conceal the presence, or absence, of a cochlear implant from device recipients and/or clinical investigators.

CONFIDENTIAL

Version 1.0 Usability of the CP950 sound processor with experienced cochlear implant users.

9.2 Visit Schedule & Procedures

9.2.1 Visit 1:

The following activities will occur during Visit 1:

- 1) Subjects will be converted from their current behind the ear sound processor (CP810 or CP900 series) to the CP950 sound processor using the recommended clinical conversation parameters. An anonymous .cdx file will be sent to the Sponsor.
- 2) The Sound Processor MAP conversion will be completed using the Wireless Pod and Custom Sound version 4.
- 3) If applicable, the subjects' wireless accessories will be paired to the CP950 Sound Processor.
- 4) The subject will be instructed to utilize the CP950 Sound Processor, Remote Assistant or Control and wireless accessories for a minimum of 30 days +/-1 week.
- 5) The subject will complete a weekly diary documenting the CP950 Sound Processor user experience.

9.2.2 Visit 2:

The following activities will occur during Visit 2:

- 1) Datalogging for the CP950 Sound Processor will be extracted. An Anonymous .cdx file will be sent to the Sponsor.
- 2) The CP950 Take Home Use Questionnaire will be completed by the subject.
- 3) The CP950 Sound Processor will be collected from each subject.

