9.3 Summary of Data Collection Visits

	Visit 1	Visit 2
Subject Enrollment & Informed Consent	X	
CP950 Fitting & Programming	X	X (Datalogs)
Fit Wireless Accessories	X	
Collect Subject Weekly Diary	X	X
CP950 Take Home Questionnaire - Subject		X
Return of the CP950 Sound Processor		X

CONFIDENTIAL

Version 1.0 Usability of the CP950 sound processor with experienced cochlear implant users.

10. Adverse Events

An adverse event (AE) is any undesirable clinical or medical occurrence associated with the use of the device, procedure, or participation in the study, which does not result in serious injury or illness related to the surgical procedure or the device.

A serious adverse event (SAE) is any untoward medical occurrence that

- results in death
- is life-threatening
- requires inpatient hospitalization or prolongation of existing hospitalization
- results in persistent or significant disability/incapacity
- requires medical or surgical intervention to prevent life-threatening illness or injury or permanent impairment to a body structure or a body function
- leads to fetal distress, death, or congenital abnormality or birth defect
- is a medically important event or reaction

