11.2 Discontinued Subjects

Any subject may voluntarily discontinue the study at any time without prejudice. The Investigator may discontinue a subject from the study at any time if (s)he considers that remaining in the study compromises the subject's health or the subject is not sufficiently cooperative. In either event, reason(s) for discontinuation should be recorded on a study withdrawal form, provided as part of the CRFs for the study. Possible reasons for study discontinuation include the following:

- AE necessitating discontinuation from the study
- The subject is lost to follow-up
- Voluntary decision to withdraw consent made by the subject
- Investigator decision
- Other reason

In case of a subject lost-to-follow-up, the Investigator must attempt to contact the subject (or relative/family contact) by phone, email or letter at least three times. If attempts are unsuccessful, the 'subject withdrawal' form is to be completed in the study file and reported, as appropriate, in required reports to the Sponsor and IRB.

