12.1 Statistical Analysis

All subjects who are consented into the clinical study will constitute the intention-to-treat (ITT) population for the purposes of safety evaluation. Only subjects fit with the CP950 Sound Processor and completed per the protocol will be considered as the completed cases (CC) population and per protocol (PP).

Demographic and outcomes data will be tabulated individually along with group summary descriptive statistics.

Descriptive statistics will be summarized for the following assessments:

- CP950 Take Home Questionnaire for existing cochlear implant users
- The number of connections as well as the success or failure of those connections to both the Wireless Pod and Wireless Accessories will be captured

CONFIDENTIAL

Version 1.0 Usability of the CP950 sound processor with experienced cochlear implant users.

- Field use data such as Time on Air, Listening Environment, Program Usage, and Accessory Use

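### The primary questionnaire is scheduled only at Visit 2, so a fitted subject who leaves earlier because of the device has no scheduled primary endpoint assessment

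*Protocol*

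**What the plan says.** The Synopsis defines the primary endpoint as "Patient reported satisfaction of the CP950 sound processor as measured by the CP950 Take Home Questionnaire for existing cochlear implant users", over seven areas that include hearing performance, retention and comfort, and reliability. Section 3 has the "CP950 Take Home Questionnaire distributed to each subject after approximately 4 weeks of take home use with the CP950 Sound Processor". Section 9.2.2 places it at Visit 2: "The CP950 Take Home Use Questionnaire will be completed by the subject". The schedules in the Synopsis and in 9.3 agree.

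The other take-home sources follow the same timing. Also at Visit 2, "Datalogging for the CP950 Sound Processor will be extracted". The 9.3 row "Collect Subject Weekly Diary" is marked at Visit 1, which is the fitting visit, and at Visit 2.

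Section 11.2 foresees early exit through an adverse event, loss to follow-up, withdrawal of consent, an investigator decision or another reason. On data it says: "In either event, reason(s) for discontinuation should be recorded on a study withdrawal form, provided as part of the CRFs for the study". For subjects lost to follow-up it adds contact attempts, but no outcome assessment.

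Section 12.1 names the "intention-to-treat (ITT) population for the purposes of safety evaluation". On its other set it says: "Only subjects fit with the CP950 Sound Processor and completed per the protocol will be considered as the completed cases (CC) population"; the same subjects form the per-protocol set.

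**The concern.** Section 3 makes acceptable retention and hearing performance a condition for the new configuration. A fitted subject who gives up the processor for one of these reasons holds direct evidence on the question the study asks, yet the plan schedules no point at which that subject rates the device. Missingness would then depend on the outcome: those most likely to rate the device poorly would be those without a rating.

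This is a matter for the protocol rather than the analysis plan. An analysis plan can choose a population or a rule for missing data, but it cannot create questionnaire answers that the visit schedule never called for. At stake is how far the descriptive satisfaction summary represents everyone who was fitted.

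**Working it through.** **1. The plan's own figure.** Section 12.2 gives about an 80% probability of seeing at least one major usability issue with n = 30 and a population rate of 5.4%. Check: 1 − (1 − 0.054)^30 = 1 − 0.946^30 = 0.811. The figure reproduces and is not in dispute.

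**2. What is scheduled for a fitted subject who leaves before Visit 2.**

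| Source | Scheduled collection after fitting | Scheduled at early exit? |
|---|---|---|
| Take Home Questionnaire (primary) | Visit 2 (9.2.2, 9.3) | No |
| Datalog | Visit 2 (9.2.2, 9.3) | No |
| Weekly diary | Visit 2 (9.3) | No |
| Withdrawal form | At discontinuation (11.2) | Yes, reason only |
| Adverse Event form | When an event is reported or observed (10.1) | Yes, if there is an event |

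The last two rows can show that a subject left and why. Neither contains ratings in the seven areas.

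**3. How much is left open, with no assumption about satisfaction.** Suppose all 30 planned subjects are fitted, k of them have no questionnaire, and x of the 30 − k completers are satisfied. The satisfied share of all fitted subjects lies between x/30 and (x + k)/30, a width of k/30:

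- k = 0: 0 points
- k = 1: 3.3 points
- k = 2: 6.7 points
- k = 3: 10 points

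Example: 24 of 27 completers satisfied is 24/27 = 88.9%. With k = 3, the share among all 30 lies between 24/30 = 80% and 27/30 = 90%. The protocol allows up to 30 subjects; with n fitted, each missing questionnaire leaves 1/n open, so 1/30 is the smallest step.

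**4. Illustration of the shift, with assumed rates.** Let s be the satisfied share among completers and d that among early leavers. The all-fitted share is [(30 − k)s + kd]/30 = s − (s − d)k/30, so the completers' figure exceeds it by (s − d)k/30. Taking s = 0.8 to 0.9:

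| k | d = 0 | d = 0.4 |
|---|---|---|
| 0 | 0 | 0 |
| 1 | 2.7 to 3.0 points | 1.3 to 1.7 points |
| 2 | 5.3 to 6.0 points | 2.7 to 3.3 points |
| 3 | 8.0 to 9.0 points | 4.0 to 5.0 points |

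The values of k, s and d are assumptions. The protocol gives neither a dropout rate nor a cut-off for counting a subject as satisfied.

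**The case against.** The strongest reply is that device-related exits would not be hidden. Section 10.1 requires an Adverse Event form for any adverse event and for adverse device effects, the withdrawal form belongs to the CRFs, and section 12.1 tabulates outcomes individually as well as by group. With at most 30 subjects, a reader of the listings would see that someone left and why. That stands, and it limits the harm. It does not supply the missing ratings: adverse events are clinical or medical occurrences, so dislike of the look, trouble with the remote control or a processor that falls off harmlessly need not be one.

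It is also fair to say that the protocol does not forbid an early questionnaire, and that a returned processor's log or diary pages might survive in practice. A reader might infer that early leavers are certain to have no data at all. The text supports only that none is scheduled.

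The remedy has limits too. Subjects lost to follow-up or withdrawing consent may still give nothing, and ratings after a few days may not be comparable with those after about four weeks, particularly for reliability and maintenance. The questionnaire itself is not in the protocol, so its suitability for early use cannot be judged. This argues against pooling early responses with the planned ones, not against collecting them.

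**Conclusion.** The gap in collection is real. Followed as written, the plan schedules no primary assessment for a fitted subject who leaves before Visit 2 because of the device. If such exits occur, and if those leavers are less satisfied than completers, the completers' summary will be too favourable. The size is unknown: 3.3 points of the all-fitted share are left open per missing questionnaire with 30 fitted, and nothing is lost if nobody leaves early. A subject who stops wearing the processor but attends Visit 2 still has the questionnaire scheduled there and is not affected.

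Two stronger readings are tempting, and the protocol does not support them:

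- **Analysis set.** A reader might infer that section 12.1 is at fault for not naming the set for the questionnaire. That choice can properly be left to an analysis plan.
- **Detection probability.** A reader might infer that the 80% in section 12.2 is weakened. That statement does not say issues are observed only through the questionnaire, so no loss follows.

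The study is descriptive with no success threshold, so no test or decision rule changes. This is a cheap improvement to the primary summary, not a flaw that invalidates it.

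**What to change.** In 9.2 and 11.2, add that when the processor is returned before Visit 2, the Take Home Questionnaire is completed where possible and where the subject agrees, with time of use recorded. The datalog should be extracted and the diary collected at the same return.

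In reporting, show these early responses separately beside the four-week summary. Give with them the number of device-related discontinuations and the reasons, with all fitted subjects as the denominator.

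The cost is a few sentences of protocol wording and a little time at an early return, with no extra subjects and no new instrument. Early responses will reflect shorter use, some leavers will still be missed, and results may look slightly less favourable.

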9.3 Summary of Data Collection Visits

	Visit 1	Visit 2
Subject Enrollment & Informed Consent	X	
CP950 Fitting & Programming	X	X (Datalogs)
Fit Wireless Accessories	X	
Collect Subject Weekly Diary	X	X
CP950 Take Home Questionnaire - Subject		X
Return of the CP950 Sound Processor		X

CONFIDENTIAL

Version 1.0 Usability of the CP950 sound processor with experienced cochlear implant users.

10. Adverse Events

An adverse event (AE) is any undesirable clinical or medical occurrence associated with the use of the device, procedure, or participation in the study, which does not result in serious injury or illness related to the surgical procedure or the device.

A serious adverse event (SAE) is any untoward medical occurrence that

- results in death
- is life-threatening
- requires inpatient hospitalization or prolongation of existing hospitalization
- results in persistent or significant disability/incapacity
- requires medical or surgical intervention to prevent life-threatening illness or injury or permanent impairment to a body structure or a body function
- leads to fetal distress, death, or congenital abnormality or birth defect
- is a medically important event or reaction

